4. METHODS

A. SWEET INTERVENTION

The SWEET intervention is described in Appendix 1. In brief, it includes five elements:

- An animation focussing on necessity of taking AET, common concerns that women have about AET and practicalities of taking AET; this will be provided to women prior to the consultation in step (ii);
- (ii) A consultation with a "HT navigator" (SWEET study nurse), tailored to an individual woman's initial experiences of AET, necessity beliefs and concerns either delivered by delegated SWEET study nurse(s) at site, or through Breast Cancer Now as per site agreement
- (iii) A web-app, containing information, tools to support adherence, and signposting to support;
- (iv) A follow-up consultation with the SWEET study nurse (either face to face, by telephone or video-call) to address any emerging concerns and problems;
- (v) Regular, brief, motivational messages delivered by email or text, promoting adherence and encouraging use of the web-app in the event of any questions or problems.

B. METHODOLOGY AND STUDY DESIGN

We will use mixed-methods to explore acceptability and feasibility issues, including:

- (i) Can we identify and recruit potentially eligible patients?
- (ii) Is it feasible to deliver the initial intervention consultation within 8 weeks of recruitment?
- (iii) Are the baseline and follow-up questionnaires acceptable?
- (iv) Do women find the intervention acceptable and useful?

(v) What is the timeliness and quality of primary care prescription encashment data and/or GP prescribing data, and is it possible to use to compute an objective measure of adherence to AET?

Sub-study 1 is a single arm, non-randomised feasibility study to explore the acceptability and feasibility of delivering the SWEET intervention. Recruited women will receive the intervention and will be followed for 7-8 weeks, at which point they will complete a follow-up questionnaire and some will undergo interviews. Interviews will also be conducted with a sample of participating health professionals (n=8-15).

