Women identified via Identification Option 1: In most instances, we anticipate that eligible women will be approached and provided with the Participant Information Sheet (PIS) at a clinic appointment (Document: *Sub-study 1 Participant Information Sheet*). The initial contact will be made by a research nurse or another member of the hospital team. If not already available, telephone numbers will be obtained for women who are potentially interested in taking part.

At least 24 hours after the receipt of the PIS, a research nurse (or another member of the hospital team) will telephone the woman, answer any questions and, if she wishes to take part, take informed consent (Document: *Sub-study 1 Verbal ICF*). It should be noted that if a woman is happy to be consented immediately, and the study team are satisfied the woman has fully comprehended what is being asked of her, then consent can be taken immediately without a 24 hour wait period. It is acceptable for the patient to complete the baseline questionnaires immediately after informed consent.

Alternatively, women may be sent the PIS in the post ahead of a scheduled clinic appointment. As women approached via this route will have had adequate time to consider their participation, they may be consented at the appointment (Document: *Sub-study 1 ICF*).

The woman will be asked to provide her email address and a phone number. If the woman does not wish to take part, the reason for declining will be recorded on a screening log (Document: *Sub-study 1 Decliners Log*). These reasons will be monitored to identify any issues or common trends that could inform the future design for an RCT.

The woman's appointment with the SWEET study nurse will be confirmed by telephone, email or post by the SWEET Study Nurse. If a site is using the Breast Cancer Now (BCN) support model, the patient details will be shared with the BCN-employed SWEET Study Nurse(s) who will arrange this appointment with the patient. Under both models, the baseline questionnaire and link to the animation will be sent by email or post by the research nurse, dependent on patient preference (see below) (Document: Sub-study 1 Baseline Questionnaire Pack).

For consented women, the site will inform participants' GPs that they are in the study and receiving an intervention to encourage and support hormone therapy adherence (Document – *Sub-study 1 GP letter*).

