Women identified via Identification Option 2: A research nurse, or another member of the hospital team, will send a letter of invitation to each woman, signed by her consultant, and enclosing the PIS, ICF and baseline questionnaires (Document: *Sub-study 1 Letter of Invitation*). After a few days, a research nurse or other member of the hospital team will telephone the woman, answer any questions and, if the woman wishes to take part, complete the consent process and prompt the woman to complete the baseline questionnaire as soon as able. The woman will be asked to provide her email address and a phone number in order for her appointment to be arranged. If the woman does not wish to take part, the reason for declining will be recorded, using a standard proforma (Document: *Decliners Log*).

Screening logs: For both methods of identification and recruitment, a research nurse (or another member of the hospital team) will complete screening logs documenting each potentially eligible

patient including whether the relevant clinical data could be found to determine her eligibility (e.g. T, N, grade, anti-HER2 therapy, receipt of chemotherapy), whether she was eligible and, if so, whether she was approached and consented (and, if not, reasons why will be recorded).

Allocating SWEET study nurse appointment & baseline data collection. Once recruited, each woman will be assigned an appointment slot with a SWEET study nurse, this appointment will be confirmed by email or post by the SWEET study nurse. For sites utilising the BCN support model, this will be a BCN nurse. The recruiting site will provide the patient with the baseline questionnaires, a freepost envelope if the woman prefers to complete the questionnaire on paper, and a link to the animation, which she will be asked to view before the SWEET study nurse appointment. Women will be offered the opportunity to reschedule the appointment if the timing does not suit them. Up to two reminders to complete the questionnaire prior to the consultation will be sent if needed (by email in the first instance after 7 days, and by telephone call after 14 days)) .

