The baseline questionnaire will include questions on: socio-demographics; lifestyle (e.g. smoking, alcohol consumption, physical activity); AET necessity beliefs (i.e. beliefs about the necessity of taking AET to remain healthy) and AET concerns beliefs (i.e. concerns about the negative effects of taking AET)[58]: whether they have initiated, or intend to initiate, AET; AET adherence (assessed using MARS-5)[69]; and cancer-specific HRQoL (assessed using the FACT-G)[60]; and utility (as measured using the EQ-5D-5L) [61] and an additional health service resource use questionnaire, based on a modified version of the UK Cancer Costs Questionnaire [62]). Baseline and follow-up questionnaires (Document: *Sub-study 1 Baseline Questionnaire Pack* and *Sub-study 1 Follow-up Questionnaire Pack*) were developed with input from the SWEET Patient Advisory Group (PAG)

Relevant medical details for each woman as included on the baseline case report form will be abstracted from medical records by the research nurse or another member of the hospital team. It will be made clear on the PIS and consent form that participation in the study involves agreeing to the individual's medical records being accessed to abstract relevant details.

Delivery of intervention and follow-up: Recruited women will have a consultation with the SWEET study nurse that will last approximately 30 minutes. We intend for these appointments to take place within eight weeks of recruitment and will measure the extent to which this is achieved. The appointment may take place face-to-face or by telephone/videoconferencing, depending on COVID-19 restrictions in place at the time and current practice for follow-up appointments at the relevant site and logistical considerations. Any consultation by SWEET study nurses via the BCN model will always be performed remotely. If a woman does not attend the appointment, she will be sent a second appointment with the option to reschedule again if the date or time does not suit.

Prior to the appointment, the woman will be set-up with an account on the HT&Me web-app using her email address. The woman will be provided with a dummy password which can be changed later if she wishes.

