In terms of AET adherence, the underpinning is provided by the Perceptions and Practicalities Approach (PAPA). The NICE Medicines Adherence Guidelines [40] recommends PAPA as an overarching framework for developing, and providing, adherence support. PAPA views adherence as a variable behaviour rather than a trait characteristic. It takes a 'no-blame' approach to non-adherence that encourages honest disclosure and then tailors support to address specific perceptions (e.g. beliefs about the treatment and condition) and practicalities (e.g. capabilities and resources) influencing the patients' motivation and ability to start and continue with treatment [68]. The core principle is that adherence support must take account of the patient's evaluation of the treatment addressing two adherence-related beliefs: necessity and concerns (The Necessity Concerns Framework (NCF)) [69]. The NCF and Leventhal's Common Sense model [70] can be applied to address salient adherence-related perception. Alongside this, it is also important to address practical issues that might impact on an individual's ability to adhere (e.g. having an adequate supply of the medication).

Focus and elements of intervention

The focus of the HT&Me intervention is on preventing non-adherence. Starting AET is a potential teachable moment when women may be more receptive to adherence support shaping their AET beliefs. We will create a common-sense rationale early on in a woman's course of AET for why it is important to take the medication, and continue long-term. The intervention addresses practical issues that inhibit adherence, and women's perspectives of AET, from the outset of treatment; this means that support can be provided to overcome misconceptions and barriers and address specific concerns that would otherwise lead to non-adherence.

Informed by our preparatory work, the intervention comprises two elements: front-loading and lighter-touch (nudge-like) follow-ups, supplemented with a web-app. Within these two elements, the intervention will have five components.

(i) Animation

This is a short video (approximately 5 minutes) which addresses necessity for AET and common AET concerns and supports self-efficacy, motivation, goal-setting and developing an adherence habit. This will be provided to women with the details of the initial SWEET study nurse appointment.

This video was developed with input from the SWEET PAG and Clinical Reference Group.

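### Section 4F sets no order between the baseline questionnaire and the animation, so some women can report baseline beliefs after seeing an intervention component aimed at those beliefs

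*Protocol*

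**What the plan says.** All places are in the protocol.

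- **The animation is intervention.** Section 4A lists it as element (i) of five: "An animation focussing on necessity of taking AET, common concerns that women have about AET and practicalities of taking AET". Appendix 1 describes it as a video of about five minutes "which addresses necessity for AET and common AET concerns and supports self-efficacy, motivation, goal-setting and developing an adherence habit".
- **The baseline measures the same constructs.** Under section 4F the questionnaire covers "AET necessity beliefs (i.e. beliefs about the necessity of taking AET to remain healthy) and AET concerns beliefs", whether the woman has started or means to start AET, and MARS-5 adherence. It also has items the animation does not target, such as socio-demographics and resource use.
- **Provision of both.** For Option 1 women, section 4F says: "Under both models, the baseline questionnaire and link to the animation will be sent by email or post by the research nurse". The later paragraph on baseline data collection repeats for recruited women in general that the site provides the questionnaires and "a link to the animation, which she will be asked to view before the SWEET study nurse appointment".
- **Deadlines.** For the questionnaire: "Up to two reminders to complete the questionnaire prior to the consultation will be sent if needed", by email after 7 days and by telephone after 14. For the consultation: "We intend for these appointments to take place within eight weeks of recruitment".
- **Partial safeguards.** Option 1 women may fill in the baseline straight after consent, but need not. Option 2 women receive the questionnaire with the invitation letter, where no animation link is listed among the enclosures, and are prompted on the consent call to complete it soon.

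**The concern.** A baseline should be measured before any part of the intervention is received. Here one intervention component and the measurement of its target share a single deadline, the nurse consultation, and nothing in the visible text puts the measurement first. A short video may well be opened before a pack of several instruments. Baseline necessity and concern scores, and possibly reported intention and adherence, would then mix women measured before exposure with women measured after it, and the mix would be unknown.

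Two things are at stake. One is how the descriptive baseline belief scores are read. The other is the process itself: section 3 lists trying out the collection of self-report data, and refining the plan of evaluation before the RCT, among the objectives of Workstream 2. Baseline collection is therefore one of the processes under test.

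**Working it through.** The point concerns the order of procedures. The plan gives no figure to reproduce, so the check sets the passages side by side.

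1. **Is the animation exposure?** Yes. Section 4A and Appendix 1 both make it a component of the intervention and name necessity and concerns as its targets.
2. **Does the baseline measure those targets?** Yes (section 4F, questionnaire content).
3. **Which comes first?**
   - *Option 1:* questionnaire and link both come from the research nurse after recruitment. Viewing is due before the appointment, and so is the questionnaire. No order is set between them.
   - *Option 2:* the questionnaire arrives before recruitment and the link after it. This favours the right order, but a woman who has not returned the questionnaire when the link arrives can still watch first.
4. **How long is the window?** The consultation is intended within 8 × 7 = 56 days of recruitment. If both items are sent at recruitment, a woman still outstanding at the second reminder may have held the link for 14 days, and up to 56 − 14 = 42 days may remain before the consultation.
5. **Can the order be recovered later?** Not from anything specified. The nurse's guide in Appendix 1 asks whether the woman received and watched the video, not when. The analytics in section 4F are described for use of the web-app, and the protocol does not say that viewing through the separate link is dated.

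**Possible size (assumption only).** If a proportion *p* of women watch first and the animation moves a belief score by *d* SD, the mean baseline shifts by *p* × *d*. The documents give neither value. With *p* = 0.5 and *d* = 0.2 to 0.3, the shift is 0.5 × 0.2 = 0.10 SD to 0.5 × 0.3 = 0.15 SD. The standard error of a mean from 45 women is 1/√45 = 0.149 SD, so even under these assumptions the shift is at most about one standard error. The finding does not depend on this illustration.

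**The case against.** The strongest reply is that nothing this study sets out to report depends on a clean baseline. Sub-study 1 is single arm. Section 4B asks whether the questionnaires are acceptable, and section 4F gives the purpose of the follow-up adherence and mediator measures as acceptability, response rate and completeness. No baseline-to-follow-up change is planned. That stands, and it limits the point to a minor one.

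Other parts also stand:

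- The text does not say that the questionnaire and link travel in one mailing. Appendix 1 ties the animation to the appointment details, which the study nurse confirms separately. All that can be said is that both are provided without a set order.
- The Option 2 sequence is a partial safeguard. A difference in order between the two routes is no defect in itself, because no comparison by route is planned.
- Flowchart 1 and the Baseline Questionnaire Pack are not shown and could carry completion instructions, so the finding holds for the protocol text only.
- Discarding questionnaires completed after exposure would conflict with their use for response rate and completeness, and making the link wait indefinitely for a questionnaire would interfere with a test of delivery.

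The reply does not remove the gap. Permission to complete the baseline after consent is not a requirement, and a prompt to complete it soon sets no order relative to the animation.

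**Conclusion.** The point holds as a minor procedural weakness. As section 4F is written, some women, mainly from Option 1, can complete the baseline measure of necessity and concern beliefs after viewing a component that targets those beliefs, and the order would not be known. The documents do not allow the number of such women or the shift in scores to be estimated.

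A reader might infer more, but the protocol does not support it:

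- *That the change in mediators will be understated.* This protocol states no analysis of change. Only a descriptive comparison made afterwards would be affected, and only if the animation moves beliefs in the intended direction.
- *That the flaw is built into the RCT.* The protocol covers Workstream 2 only and does not describe RCT baseline procedures. If the same sequence were used there and only the intervention arm received the animation, baseline beliefs could differ by arm and adjusting for them could remove part of the effect on mediators. That is conditional.
- *That the study cannot proceed without a change.* The feasibility outputs are affected little or not at all.

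**What to change.** In section 4F, for both identification routes:

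1. Send the animation link once the baseline questionnaire is submitted (a REDCap trigger; section 5H already has women entering data there directly) or once the paper form is received.
2. If the questionnaire is still outstanding after the second reminder, send the link anyway before the appointment, so that no woman loses the component.
3. Record the date the questionnaire was completed and the date the link was sent.
4. Keep all returned questionnaires for response rate and completeness. When describing baseline beliefs and adherence, flag those completed after the link was released as post-exposure.

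Appendix 1 also places the animation in the web-app, and section 4F sets up the account before the appointment. The same rule should therefore govern when log-in details are released.

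The cost is a wording change, one automatic trigger and a second mailing for women who use paper. Slow responders receive the animation some days later, still before the appointment, and Appendix 1 already allows viewing at the consultation where it has not been seen. Sample size and intervention content do not change.

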5. ETHICAL AND REGULATORY CONSIDERATIONS

A. CONSENT

Participation in sub-studies 1 and 2 will be contingent on informed consent being obtained. Prior to expressing their interest in participating, all potential participants will be provided with the appropriate participant information sheet detailing the study objectives and what taking part will involve.

All potential participants will have the opportunity to ask questions using contact details provided and will be given at least 24 hours between being provided with the information about the study and

being asked to provide consent (if participant is happy to be consented immediately, and the study team feel they fully understand what is being asked of them, then consent can be taken without a 24 hour wait period). Immediately prior to being asked to provide informed consent, participants will be given further opportunity to ask any questions.

Participants will be informed that participation is voluntary and that they can withdraw from the study at any point, without affecting their medical care or legal rights. It will be made clear that any information arising from the study will be anonymised so they will not be identifiable in any publications or report. Participants will be asked to indicate their understanding that this anonymous information may be used in future related research, or may be shared with other researchers working in collaboration with the research team, including students.

Written consent will be obtained from those being consented in person. For those from whom consent is obtained by phone or video conference interviews, the verbal consent form will be used, in adherence with Sponsor SOPs.

The timing of consent for substudies 1 and 2 is described under section 4F.

B. ASSESSMENT AND MANAGEMENT OF RISK

Sub-study 1: It is possible that participation in sub-study 1, particularly the qualitative interviews, may have emotional consequences for women with breast cancer and may involve them considering and discussing potentially upsetting issues related to their own experiences.

The project leads ([name] & [name]) and the researchers are experienced in interviewing individuals who have had cancer and/or other potentially vulnerable patient groups. If an interviewee does not wish to answer any question during the interview, this will be respected. If the interviewee becomes upset, the researcher will ask them if they wish to stop the interview, either temporarily or permanently. Moreover, if an interviewee becomes very distressed, the researcher will ask whether they would like them to contact someone (e.g. a family member, friend, GP, or clinician) on their behalf. A similar process will be followed in the event that a participant becomes distressed during either the initial SWEET study nurse appointment or the follow-up call.

The participant information sheets will contain information about who (patient) participants might contact if they feel they want to discuss any issues arising from taking part in the study. For example, this will suggest that they contact the research team, their GP, their clinical team in the hospital, and will direct interviewees to information and helplines such as those offered by Breast Cancer Now and Mind.

Sub-study 2: No data will be collected directly from participants themselves – they will simply be asked for consent for access to their medical records and for linkage to national datasets. The participant information sheet will contain information about who they might contact if they feel they want to discuss any issues arising from agreeing to take part in the study. For example, this will suggest that they contact the research team, their GP, their clinical team in the hospital, and direct interviewees to information and helplines such as those offered by Breast Cancer Now and Mind.

C. RESEARCH ETHICS COMMITTEE REPORTING

Ethical approval will be obtained from a UK Health Department's Research Ethics Service NHS Research Ethics Committee (REC) for the study protocol, informed consent forms, participant information sheets and other study materials.

Substantial amendments that require review by NHS REC will not be implemented until that review is in place and other mechanisms are in place to implement at site. All correspondence with the REC will be retained. The chief investigator will organise the production of research reports as required and notify the REC of the end of the study. An annual progress report will be submitted to the REC within 30 days of the anniversary date on which the favourable opinion was given, and annually until the study is declared ended. If the study is ended prematurely, the Chief Investigator will notify the REC, including the reasons for the premature termination. Within one year after the end of the study, the Chief Investigator will submit a final report with the results, including any publications/abstracts, to the REC.

D. REGULATORY REVIEW AND COMPLIANCE

Before any site can enrol patients into sub-study 1 or sub-study 2, the Chief Investigator or a designee will ensure that appropriate approvals from participating organisations are in place.

For any amendment to the study, the Chief Investigator or designee, in agreement with the sponsor, will submit information to the appropriate body for them to issue approval for the amendment. The Chief Investigator or designee will work with sites (R&D departments at NHS sites) so they can put the necessary arrangements in place to implement the amendment and to confirm their support for the study as amended.

E. AMENDMENTS

If a substantial amendment to the REC application or the supporting documents is required, approval will be sought from the sponsor before submitting a notice of amendment to the REC for consideration. The sponsor will categorise the amendment as substantial or non-substantial. The Health Research Authority will be informed.

Substantial and non-substantial amendments will be communicated to the participating organisations (R&D office and local research team) departments of participating sites to assess whether the amendment affects the NHS permission for that site. Some amendments that may be considered to be non-substantial for the purposes of REC may still need to be notified to NHS R&D (e.g. a change to the funding arrangements).

The Chief Investigator will be responsible for the decision to amend the protocol and any supporting documents. The amendment history will be logged in the site-files. The protocol and all supporting documents will be version tracked, so that the most recent versions can be identified easily.

F. PEER REVIEW

The project has been funded by the National Institute for Health Research (NIHR). The funding application for this project was independently peer reviewed by several independent experts and by The NIHR Programme Grants for Applied Research funding panel. It has also been reviewed by independent breast cancer experts on the National Cancer Research Institute (NCRI) Breast Cancer Group, and experts in cancer survivorship research on the NCRI Psychosocial Oncology & Survivorship Group.

G. STAKEHOLDER AND PATIENT AND PUBLIC INVOLVEMENT

In developing the larger NIHR programme grant proposal we recruited two patient representatives to the team (team members [name] & [name]), who have been actively involved from the start in planning meetings and commenting on iterations of the proposal. They have also consulted widely with members of local support groups, their own social networks, colleagues on the NCRI Consumer Forum and through Independent Cancer Patient Voices and have actively fed views back into the development process.

When the programme began, we established a Patient Advisory Group (PAG) which includes a diverse group of 11 women with a range of experiences of AET. User co-applicants co-chair the PAG group and also sit on the study Programme Management Committee (PMC). The PAG meet regularly and have been closely involved in co-designing the intervention web-app and in developing the scripts for the initial and follow-up consultations. They have also reviewed the patient-facing documents for the feasibility study and provided input to the choice of questionnaires for assessing outcomes and mediators. For the later stages of the programme (i.e. after these substudies), those PAG members who wish to be involved in analysis of study data will be given relevant training by team members. The PAG will also provide a patient perspective on the write-up of papers, will help produce lay summaries, and with presenting the study findings results at conferences, support groups and charity group open days.

PAG members receive payment for their time in line with NIHR INVOLVE recommendations and receive reimbursement for travel and any carer expenses.

We also established a wider PPI group called a Community of Interest (CoI). The CoI includes 30 women with breast cancer who have been prescribed AET. The CoI is consulted, mainly by email, on an ad hoc basis, as and when needed. They were extensively consulted in the development of content for the web-app and several members of the group pre-tested the web-app.

Beyond PPI, we have also engaged extensively with a wide range of stakeholders. In developing the programme, we sought advice from consultants in breast cancer, breast cancer nursing groups (e.g. Pan London Breast Care Nurses) and the third sector (Breast Cancer Now, Macmillan Cancer Support). The programme has the support of the NCRI Breast and Psychosocial and Survivorship Groups and Breast Symptoms Working Group.

During the programme, we have established a Clinical Reference Group which includes breast cancer surgeons, oncologists, GPs, pharmacists, cancer specialist nurses, community nurses, and a clinical psychologist and a dietitian with expertise in breast cancer. We consult with this group regularly, including on eligibility criteria, clinical aspects of the intervention content, and the content of the navigator appointments.

We also work closely with Breast Cancer Now, who are partners in the programme.

H. DATA PROTECTION AND PATIENT CONFIDENTIALITY

Data controllers and regulatory compliance: The Newcastle upon Tyne Hospitals NHS Foundation Trust (NuTH) is Sponsor for the study and will act as data controller. All investigators, researchers and study site staff will comply with the requirements of the Data Protection Act 2018, with regards to the collection, storage, processing and disclosure of personal information and will uphold the Act's core principles and General Data Protection Regulation (GDPR).

Recruitment of patient participants (sub-study 1 & 2): The local clinical team will act as 'gate keepers' and eligible patients will be initially informed of the study via their healthcare professionals. The research team (including where BCN are involved) will not have access to contact details for any patient participants, until they themselves give their permission, provide their details directly, or indicate to the relevant member of the clinical team that they are happy for their details to be passed onto the researcher.

Identifiable data, consents, screening logs and decliners log: Any identifiable data will be stored securely on an NHS network. We will utilise the REDCap software hosted by the Newcastle upon Tyne Hospital NHS Foundation Trust, which is HSCN compliant. This database will also include clinical details extracted from women's medical records for the purpose of the study. Those at clinical sites (e.g. Research nurses) will only be able to access the details of women recruited through their site. A small number of designated members of the research team will be able to access identifiable and contact information on all women recruited as required for specific purposes (e.g. delivering the intervention, sending questionnaires, arranging interviews, sending summary of findings). Any other members of the research team who required access to the database will only be able to see anonymised information.

Screening logs & the decliners log will be held in site files with copies (excluding identifiable details) held at Newcastle University.

Paper records of consent, which contain names or study IDs, will be kept at site for five years following the end of the study in order to allow for audit of the research process if required. No other personal data such as contact details will be kept longer than is necessary and any identifying information will be anonymised in the data for analysis.

Questionnaires (sub-study 1): Questionnaires will be identified by study ID numbers only. The patient will either enter the data directly onto the patient facing database (REDCAP) or if they use paper copies, these will be stored at site and entered onto REDCAP for the central research team to access for the purpose or analysis

Interviews and consultations (sub-study 1): Paper copies of the details of the SWEET study nurse consultations (including date delivered and checklist of items covered) will be entered by site to REDCAP (in the case of BCN involvement, these details will be provided to site for input). The audiorecordings of the interviews and SWEET nurse consultations will be stored on a secure part of the Newcastle University network (SWEET OneDrive), with access restricted to designated members of the research team. Transcription of the interviews will be undertaken by a member of the research team or an external company, Type it Write (TiW). TiW will be asked to sign a Non-Disclosure Agreement. Sending interview recordings to TiW and receipt of transcripts will follow a defined protocol (Document: *Sub-study 1 Transcription Protocol*). Files to be transcribed will be saved in a password-protected, encrypted zip folder and immediately uploaded to TiW using their file upload service. The password will be provided to the service separately by email.

Recordings will be retained until the end of sub-study 1 to allow researchers to return to the data as needed. Following this they will be permanently deleted.

Interview transcripts (sub-study 1) will be anonymised (e.g. removing places, names) and stored on a secure part of the Newcastle University network (SWEET OneDrive). Each transcript will be saved with the individual's unique study ID number.

Digital analytic data (sub-study 1) will be stored in the cloud, using UK-based servers only (Azure Cloud). Any personal identifiable information recorded will be pseudonymised and stored separately

from the information relating to the woman's use of the application. The pseudonymised personal data will be deleted once the analysis has been completed.

Pseudonymised prescription data (sub-study 2) returned to the study team by NHS Digital (or from participants' GPs) will be stored on a secure location on the Newcastle University network. Access will be restricted to specified members of the research team who require access for the purposes of the study.

Site files will be held by the Principal Investigator for each clinical site in a lockable office. This folder will contain essential documents as well as recruitment and screening logs for the study site (who has been approached/written to about the study) and consent forms.

Archiving: After each study has ended, anonymised data will be archived in line with Sponsor policy once the final report and publication are complete. Research data will remain available for 5 years following any publication, after which retention will be reviewed.

Data sharing: The consent procedures include informing participants about the sharing of data and make clear that only their fully anonymised information will be used in future relevant research or shared with other researchers outside of the immediate research team.

I. ACCESS TO THE FINAL STUDY DATASET

Sub-study 1: The final data set will be accessible by the research team; anonymized data may be made available to other researchers, including students, for secondary analysis. The consent procedures include consent for the sharing of data. It will be explained to participants verbally and in writing, that anonymised data may be shared in future for relevant research by other researchers working in collaboration with the research team.

Sub-study 2: The final pseudonymised dataset will be accessible only to members of the research team.

J. DISSEMINATION AND OUTPUTS

Our dissemination strategy includes conference presentations, scientific papers, regular social media and lay communications, and briefings (paper, digital and events) for clinical teams, patient groups and commissioners.

We are establishing a SWEET programme website. The website will contain information for both scientific and lay audiences, including the study protocol and a final study report. We will also design a twitter handle so that post key information, share progress and encourage engagement and debate throughout the programme.

For scientific dissemination, the research findings will be presented at relevant national and international meetings, as is possible in light of Covid-19, (e.g. National Cancer Research Institute conference, UK Society of Behavioural Medicine conference, UK Interdisciplinary Breast Cancer Symposium, European Breast Cancer Conference). Papers will be submitted to journals, for example, in cancer survivorship (e.g. J Cancer Survivorship, Support Cancer Cancer), and psychooncology/behavioural science (e.g. Psycho-Oncol, Implement Sci, Patient Educ & Counselling). Papers and conference presentations will be publicised on the project website.

For lay dissemination, research participants in sub-study 1 will be given the option of receiving a lay summary of the findings once the sub-study is completed. To reach patient and general populations, updates will be posted on the project website, with key messages (crafted together with the PPI Panel) highlighted. We may hold a dissemination event for breast cancer survivors and healthcare professionals. If there is sufficient interest, we will live stream this event to other locations (e.g. collaborating centres). We may also record parts of the event and post on the website.

